3.3.2.1 Adverse Events of Special Interest (AES/)

Adverse events of special interest (AESI) are those that require special collection and/or reporting. They are not necessarily those expected to be related to study drug or those most frequently occurring.

The following adverse events have been identified as an important medical risk:

AESI	Definition
Ocular adverse events related to vitamin A deficiency	AE with Higher level term (HLT): Fat soluble vitamin deficiencies and disorders; or
	AE with PT: Vitamin A decreased; or AE with PT: Vitamin A abnormal; or
	 AE within the Structured MedDRA query (SMQ): Optic nerve disorders; or AE within the SMQ: Corneal disorders; or AE within the SMQ: Retinal disorders.
Thrombocytopenia	AE with HLT: Thrombocytopenias; or AE with HLT: platelet analyses
Renal Impairment	AE within theSMQ: Acute renal failure

3.3.2.2 Other Adverse Events of Interest

The following list includes other adverse events that have been identified to be of interest:

Other AEs of interest	Definition
Coagulation abnormalities	AE with HLT: Coagulopathies
Abnormal liver function	AE within the SMQ: Drug related hepatic disorders - comprehensive search
Adverse events at the injection	AE with HLT: Injection site reaction; or
site	AE within HLT: Administration site reaction NEC.
Flu-like symptoms	AE with PT: Influenza like illness; or

Other AEs of interest	Definition	
	AEwith PT: Pyrexia (or Feeling hot or Body temperature increased) plus at least one of the following symptoms:	
CNS disorders	AE within System Organ Class (SOC): Nervous system disorder	
Haemorrhages	AE within the SMQ: Heamorrhages	
Potential complement activation	AE within SMQ: Hypersensitivity	
Reduced thryroxine	AE within SMQ: Hypothyroidism	

Results by type of haemorrhagic eventsmay be provided; the type of haemorhagic events and respective definitions will be pecified prior to database lock.

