2. BACKGROUND AND RATIONALE

2.1 Overview of Disease

Transthyretin is synthesized primarily in the liver and is secreted into the plasma as a 55 KD protein composed of 4 identical subunits of 14 KD each. A major function of TTR in the plasma is to transport retinol (vitamin A) to tissues through an association with RBP4. Transthyretin amyloidosis is a rare hereditary disease caused by mutations in the TTR protein. The disease causing mutations destabilize the normal tetrameric structure of TTR causing its dissociation into free monomers and subsequent aggregation into insoluble fibril deposits. These deposits are found in multiple organs including the peripheral nervous system, gastrointestinal tract and heart. They result in local damage to cells leading to a peripheral polyneuropathy (called Familial Amyloid Polyneuropathy or FAP) and a cardiomyopathy (called Familial Amyloid Cardiomyopathy or FAC). FAP can be classified into 3 stages of disease based on ambulatory status: Stage 1 – do not require assistance with ambulation; Stage 2 – require assistance with ambulation; Stage 3 – wheelchair bound (Coutinho et al. 1980). The total worldwide prevalence of FAP has been estimated at approximately 10,000 patients (Coelho et al. 2008).

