2.2 Therapeutic Rationale

ISIS 420915 is an antisense drug targeted to human TTR mRNA and its hybridization to the cognate TTR mRNA results in the RNase H-mediated degradation of the TTR mRNA, thus preventing production of the TTR protein (see Section 2.3). The strategy of treating FAP patients with ISIS 420915 is to reduce the levels of mutated and wild-type TTR protein secreted by the liver. It should be noted that antisense oligonucleotides (ASOs) are highly charged hydrophilic molecules that do not cross the blood brain barrier (Levin et al. 2008) and thus systemic treatment with ISIS 420915 is not predicted to decrease levels of TTR in the brain. It is predicted that decreasing the amount of liver-derived TTR protein circulating in the plasma by treatment with ISIS 420915 will result in a decrease in the formation of TTR amyloid fibril deposits, and thus slow or halt disease progression. This strategy is a similar strategy to orthotopic liver transplantation, with the exception that ISIS 420915 reduces wild-type protein in addition to the mutated protein. Given that wild-type TTR can continue to deposit as amyloid after liver transplant, this distinction may represent a therapeutic advantage.

There is a high unmet medical need for both Stage 1 and Stage 2 FAP patients worldwide. For Stage 2 patients, there is currently no approved therapy and these patients are often not candidates for liver transplant due to advanced age, health reasons, or cardiac involvement. For Stage 1 patients, Vyndaqel® is currently the only approved therapy. However, it is only approved in some countries and is not yet widely reimbursed or established as the standard of care.

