9.4 Monitoring and Recording Adverse Events

Any pre-existing conditions or signs and/or symptoms present in a patient prior to the start of the study (i.e., before informed consent) should be recorded as Medical History and not recorded as AEs unless the pre-existing condition worsened. The exception is AEs from the parent study (ISIS 420915-CS2) that are ongoing at the time the patient enters this study. These should be recorded as ongoing AEs from ISIS 420915-CS2. The Investigator should always group signs and symptoms into a single term that constitutes a **single unifying diagnosis** if possible.

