3.3.2 Adverse Events (AEs)

Adverse events will be coded using Medical Dictionary for Regulatory Activities (MedDRA). The final version used will be designated in the clinical study report. For each AE, the severity level of the event (mild, moderate, or severe) will be determined by physician opinion.

TEAEs are defined as adverse events that first occurred or worsened after the first dose of Study Drug (ISIS 420915 or Placebo). This is the general definition of TEAEs. A detailed definition of TEAEs for safety analysis of the OLE study or for the longitudinal safety analysis will be discussed in section 3.3.2.6 or in section 3.3.2.7, respectively.

In this section, whenever first dose of ISIS 420915 is used, it refers to **CS3 Study Day 1** for OLE study analysis and **Day 1 of ISIS 420915** for longitudinal safety analysis.

An AE with a completely missing start date will be assumed to be treatment emergent.

If the maximum severity of the adverse event is greater than the baseline severity, i.e. severity prior to the first dose of ISIS 420915, or if the onset date/time is the same as or after the date/time of the first dose of ISIS 420915, then the event is considered to be treatment emergent.

In the situation where change in severity (but no change in seriousness) occurs for an adverse event, study sites are instructed to enter an end date and start a new record for the adverse event. In the new record, the changed severity is to be recorded and the start date will be set to be the end date of the previous record. Data linking those records are collected in the database. Consider three scenarios:

- The first AE record occurs prior to the first dose of ISIS 420915, the second AE record occurs on
 or after the first dose of ISIS 420915, and the severity increases: Only the second record will be
 counted as treatment-emergent.
- The first AE record occurs prior to the first dose of ISIS 420915, the second AE record occurs on or after the first dose of ISIS 420915, and the severity decreases: Neither record will be counted as treatment-emergent.
- Both records occur on or after the first dose of ISIS 420915: If the AE severity on the second record is worse than the severity on the first record, then count both records as treatmentemergent. But, if the severity improves, then only count the first record as treatmentemergent.

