Of note, when counting the total number of treatment-emergent events, events linked through change in severity will still be counted as separate events.

In addition, special considerations should be given to AEs which started in the parent study but continued at the time the patient enrolled in the OLE study. These situations may occur if the outcome of the AE is "Ongoing" or the stop date is missing in the parent study. Records for these AEs will be created in the OLE study database with a different AE index number so that they can be updated with information collected in the OLE study, e.g. stop date and treatment. The following rules describe how these AEs will be handled in the OLE study analysis for SS and the longitudinal safety analysis for LSS:

• For AEs with the same Lower level term (LLT), complete start date and severity recorded in both the parent study and the OLE study: keep the record in the OLE Analysis Data Model (ADaM) dataset, but this record is not considered treatment emergent in CS3. In the longitudinal safety analysis, this record will be counted once (it is considered treatment emergent in CS2 and therefore considered treatment emergent in the longitudinal safety analysis).

Note that an event which started during the gap period between the parent study and the OLE study will not be considered treatment emergent in the CS3 analysis, unless the severity of the event has increased after the first dose in CS3. Such events will be regarded as treatment emergent in the

longitudinal safety analysis (see below) conducted on the LSS. Since subjects randomized to placebo in the parent study are not included in the LSS, if a placebo subject from the parent study experiences such an event, that event will not be summarized in any of the CS2, CS3 or longitudinal safety analyses.

A listing will be provided stating which patients reported each preferred term. Adverse events in the following categories will be summarized separately:

- Adverse events of special interest
- · Other adverse events of interest

Summary tables of the number and percentage of patients with these adverse events will be displayed split by AEcategory and treatment group. TEAEs of special interest and other TEAEs of interest will also be summarized for patients in the CM-ECHO Set.

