3.3.2.6 OLE Study Analysis of TEAEs

TEAEs which occur during the OLE study include TEAEs which first occurred or worsened on or after **CS3 Study Day 1**. Derivation is described in Section 3.3.2.

The following categories of AEs in the OLE study will be summarized by treatment group from the parent study: all TEAEs; TEAEs leading to early discontinuation from Study Drug or from the study; and serious adverse events. The percentage of patients reporting the adverse event will be summarized by MedDRA System Organ Class (SOC) and Preferred Term (PT), and will be sorted by SOC alphabetically and then by decreasing frequency of PT within SOC.

Summaries of drug related TEAEs, TEAEs by maximum severity, TEAEs grouped by duration of exposure to the Study Drug at the start of the event (< 6 months, \geq 6 months to < 12 months, \geq 12 months to < 24 months, \geq 24 months to < 36 months, \geq 36 months to < 48 months, \geq 48 months to < 60, \geq 60 months) and Number of dose at the start of event (<26, \geq 26 to < 52, \geq 52 to < 104, \geq 104 to < 156, \geq 156 to < 208, \geq 208 to 260, \geq 260) will also be provided. Duration of exposure and the number of doses is calculated from **CS3 Study Day 1** to the start date of event.

All TEAEs will be summarized for subgroups defined by the following variables:

- Age at parent study screening (<65 years and >=65 years),
- Sex (Female and Male),
- Race (White, non-White),
- Region (North America, Europe and South America / Australasia),
- CM-ECHO Set (Included and Not Included).

As well as stratification factors at randomization during the parent study, including

- V30M TTR mutation (Yes, No),
- previous treatment with Vyndagel® or Diflunisal (Yes, No),
- Disease stage (Stage 1 and Stage 2).

Results will not be provided for a variable if the overwhelming majority of patients are within one level of the subgroup. Non-TEAEs reported will be flagged in the all AE listing.

TEAEs in the following categories will also be summarized in tables and listed separately:

- Adverse events of special interest (defined in section 3.3.2.1)
- Other adverse events of interest (defined in section 3.3.2.2)
- Local cutaneous reactions at injection site (defined in section 3.3.2.3)
- Flu-like reactions (defined in section 3.3.2.4)

Summary tables of the number and percentage of patients with these adverse events will be displayed split by AE category and treatment group received in the parent study.

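### The 'CNS disorders' category is the whole Nervous system disorder organ class, so its count mixes worsening peripheral neuropathy with central events and is not CNS-specific

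*Combined protocol and SAP*

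**What the plan says.** SAP 3.3.2.2 tabulates other adverse events of interest, each row pairing a label with a MedDRA rule. The row labelled 'CNS disorders' has the rule "AE within System Organ Class (SOC): Nervous system disorder". No preferred term, higher level term or standardized query narrows it, and no peripheral terms are excluded.

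Protocol 2.1 describes what the amyloid deposits do: "They result in local damage to cells leading to a peripheral polyneuropathy (called Familial Amyloid Polyneuropathy or FAP"). Protocol 2.2 gives the aim of treatment as to "slow or halt disease progression", so the disease is expected to progress.

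On recording, Protocol 9.4 says that pre-existing conditions "should be recorded as Medical History and not recorded as AEs unless the pre-existing condition worsened". On counting, SAP 3.3.2 says "TEAEs are defined as adverse events that first occurred or worsened after the first dose of Study Drug".

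On display, SAP 3.3.2 says "Summary tables of the number and percentage of patients with these adverse events will be displayed split by AEcategory and treatment group". It also calls for the same categories in the CM-ECHO Set. SAP 3.3.2.6 and 3.3.2.7 repeat these categories for the OLE and longitudinal analyses.

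**The concern.** The label promises a count of central nervous system events, but the rule delivers a count of all nervous system events. In many populations the gap would be a minor looseness. Here every patient has a peripheral neuropathy, so this is the population in which central and peripheral most need to be kept apart.

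Safety and tolerability are the primary objective (Protocol 1.1, SAP 1.2.1). There is no untreated control and no formal hypothesis, so descriptive counts carry the safety evidence and a count should mean what its label says. Protocol 2.2 also describes antisense oligonucleotides as "highly charged hydrophilic molecules that do not cross the blood brain barrier". A sizeable percentage in a row called 'CNS disorders' would appear to sit awkwardly with that statement when it might reflect only the disease under study.

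**Working it through.** The plan states no event rate, sample size or test for this category, so there is no figure to reproduce. The check is a reading of the rules side by side.

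1. **What the rule tests.** The only input is membership of the Nervous system disorder organ class. Whether the event is central is not an input. 'Nervous system' is wider than 'central nervous system', so label and rule differ on their face.

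2. **How the neighbouring rows are built.** SAP 3.3.2.1 has three categories and 3.3.2.2 has eight. All three of the first, and seven of the eight in the second, use higher level terms, standardized queries or preferred terms. Only 'CNS disorders' takes an entire organ class.

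3. **Whether the disease reaches the row.** FAP is a peripheral polyneuropathy (Protocol 2.1) and is expected to progress (Protocol 2.2). Worsening of a pre-existing condition may be recorded as an adverse event (Protocol 9.4). A worsened event is treatment-emergent (SAP 3.3.2). If coded to the nervous system class, it then counts as a 'CNS disorder'. The documents do not list the terms in the class. That neuropathy terms fall there is an inference from the name of the class.

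4. **What is filtered out.** Stable pre-existing neuropathy goes to medical history. An event carried over from the parent study with the same lower level term, complete start date and severity is not treatment-emergent in the OLE analysis (SAP 3.3.2). These rules remove unchanged disease and let new or worsening disease through.

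5. **Where the row is reported.** It appears in the OLE tables (3.3.2.6), the longitudinal tables (3.3.2.7) and the CM-ECHO Set tables (3.3.2). SAP 9.1, which lists analyses dropped from the final report, does not drop it.

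6. **What the row adds.** SAP 3.3.2.6 already summarizes all TEAEs by organ class and preferred term. A category defined as one whole class repeats that class's total.

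7. **Size.** Let *b* be the proportion of patients with at least one peripheral or disease-type nervous system TEAE, and *c* the proportion with at least one central TEAE. If the two are taken as independent, the row shows 1 − (1 − *b*)(1 − *c*). A change of *d* in *c* then moves the row by (1 − *b*)*d*. The central component is diluted by the factor 1 − *b* and vanishes only if *b* = 1. The documents give neither *b* nor *c*, so the factor cannot be evaluated.

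**The case against.** A reader might infer that the plan cannot show a CNS effect at all. The documents do not support that. SAP 3.3.2.6 tabulates TEAEs by organ class and preferred term, SAP 9.2.1 adds such a table by PND score, and SAP 3.3.2 promises a listing of which patients reported each preferred term. A central event would appear there under its own name. SAP 3.3.2.7 does not repeat the organ-class and preferred-term layout for the longitudinal tables, but the events themselves are not lost.

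A reader might also infer that the row is triggered simply by having FAP. It is not: only new or worsening events recorded as adverse events enter it (step 4). Nor can one say that the row will mainly measure disease progression, or attach a percentage or risk ratio to the dilution. No rate is given, not all patients reach years 4 and 5, every patient receives the drug, and the SAP plans no comparison of this category.

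The remaining defence is that this is a second-tier row, outside the important medical risks of 3.3.2.1, for a drug class said not to enter the brain, and that a broad net backed by preferred-term tables is reasonable. The low tier is a fair point and keeps this modest. A broad net is defensible too, but then the row should carry the name of the net. The SAP has already made this kind of correction: its amendment history records the complement row being renamed as potential complement activation. Finally, the lack of an untreated control limits attribution under any definition, so correcting the row does not cure that.

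**Conclusion.** The point stands as a mismatch between label and definition in a reported safety category. Followed as written, the 'CNS disorders' row gives the count for the whole nervous system class, mixing new or worsening peripheral neuropathy with central events. It should not be read as a CNS count. It adds nothing to the organ-class total already planned.

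The effect is on interpretation, not on data: no event is lost, and central terms can be found elsewhere in the output. The size of the mixing is unknown because the documents give no rates. The conclusion that the label is too narrow rests only on the wording. The conclusion that worsening FAP inflates the row rests on the further assumption that neuropathy terms are coded to the nervous system class, which should be confirmed against the dictionary version in use.

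**What to change.** In SAP 3.3.2.2, define 'CNS disorders' by a pre-specified list of central terms within the nervous system class, fixed before database lock. The section already makes this provision for types of haemorrhagic event. Show all remaining events in the class on a separate line, labelled peripheral or other nervous system events, including the disease under study. Apply the same split in the tables of 3.3.2.6, 3.3.2.7 and the CM-ECHO Set.

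If no split is wanted, the minimum change is to relabel the row 'Nervous system disorders', so that label and rule agree.

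The cost is a wording change and one term list, with no new data collection. The small downside is that a few unspecific preferred terms will need a medical decision on which line they join; that decision should be documented with the list.

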3.3.2.3 Local Cutaneous Reactions at Injection Site {LCRIS}

The following MedDRA preferred terms are determined by the Sponsor's Pharmacovigilance personnel to represent the local cutaneous reaction at the injection site:

- Injection site erythema
- Injection site swelling
- Injection site pruritus
- Injection site pain
- Injection site tenderness

Only events that start on the day of injection and persist for at least two days, i.e. event onset date on the day of injection and resolution date not on the day of injection or the day after the injection, will be included. Events with onset date on the day of injection and missing resolution date will also be included. AEs with partial or missing dates will be handled as follows. First establish whether the event is treatment emergent (Details of TEAE definition see section 3.3.2.6 for TEAE occurred during the OLE study and section 3.3.2.7 for TEAE for overall including the parent study and OLE study). If yes, then establish if the preferred terms match the ones listed in the LCRIS definition. If yes, check whether the event onset dates are within the specified time frame. If at this stage, onset date is

missing or partially missing, the event will be considered to have started within the required time frame.

The number and percent of patients in each treatment group of the parent study experiencing LCRIS will be tabulated.

Percentage of injections leading to local cutaneous reactions at the injection site will also be summarized. Percentage of injections leading to local cutaneous reactions will be calculated for each patient as (A/B)*100, where A is the number of injections with a local cutaneous reaction at the injection site, and B is the total number of injections.

3.3.2.4 Flu-Like Reactions

The following MedDRA preferred terms are determined by the Sponsor's Pharmacovigilance personnel to be the flu-like reactions:

- Influenza like illness
- Pyrexia (or Feeling hot or Body temperature increased) plus at least two of the following symptoms:
 - o Chills
 - Myalgia
 - o Arthralgia

Only events that start on the day of injection or the day after injection will be included. AEs with partial or missing dates will be handled as follows. First establish whether the event is treatment emergent (Details of TEAE definition see section 3.3.2.6 for TEAE occurred during the OLE study and section 3.3.2.7 for TEAE for overall including the parent study and OLE study). If yes, then establish if the preferred terms match the ones listed in the flu-like reactions definition. If yes, check whether the event onset dates are within the specified time frame. If at this stage, onset date is missing or partially missing, the event will be considered to have started within the required time frame.

The number and percentage of patients in each treatment group experiencing flu-like reactions will be tabulated.

The percentage of injections leading to flu-like reactions will also be summarized. The percentage of injections leading to flu-like reactions will be calculated for each patient as (A/B)*100, where A is the number of injections associated with a flu-like reaction, and B is the total number of injections.

